10.2 Analysis Populations

The following analysis populations have been defined for the study:

- Note: the **DLT Evaluable Set** (dose escalation phase) is defined in [Section 5.1.1](#).
- **Safety Analysis Set (SAS) – (All Treated Population):** This population includes all patients who have received at least one dose of surufatinib. Safety data will be evaluated based on this population's outcome. Patients in the SAS will be analyzed by their actual dose initially received. If patients have dose reduction during the study, all data will be summarized/analyzed based on the initial dose of

study drug received. Efficacy endpoints PFS and OS (OS applies to BTC and STS cohorts only) will be analyzed based on this population.

- **Pharmacokinetic Analysis Set (PKAS):** This population will include all patients who received at least one dose of surufatinib and have at least one PK sample obtained and analyzed.
- **Efficacy Analysis Set (EAS):** This population includes all patients who have received at least 1 dose of surufatinib and have had at least 1 post- baseline tumor assessment. All efficacy endpoints will be analyzed will based on this analysis set, except for PFS and OS, which will be analyzed based on SAS.

10.3 Statistics and Analysis Method

There is no formal hypothesis testing in this study. In general, the study data will be summarized descriptively by dose group and disease cohort (ie, BTC arm, pNET arm, epNET arm, and STS arm), unless otherwise specified. In general, all summaries will be presented by assigned dose level in the dose escalation phase and by disease cohort (BTC, pNET, epNET, and STS) in the dose expansion phase. Where applicable, certain summaries may be provided by STS subtypes: LMS, UPS, epithelioid sarcoma, angiosarcoma, SS, and PVNS.

A patient listing of all treated patients will be generated to describe site, patient number, screening date, first dosing date, duration of study treatment, analysis set in which the patient included and disposition. In the patient disposition listing, reason for study drug discontinuation will be included. A table will be created to summarize these categories in terms of number and percent for each of the analysis set defined above.

Patient demographics and baseline characteristics, such as age, sex, race/ethnicity, weight, type of malignancy, duration of malignancy, site of metastatic disease, and baseline ECOG performance status, will be listed and summarized. All summaries will be presented by dose level in the dose escalation phase and by disease cohort in the dose expansion phase.

Major protocol deviations related to study inclusion or exclusion criteria, conduct of the trial, patient management, or patient assessment will be listed.

Study drug administration data will be listed by dose level and by disease cohort, and any dose modifications will be flagged. Descriptive information will be provided regarding number of cycles, total duration of study drug exposure, actual duration of study drug taken, cumulative dose of study drug, dose intensity and relative dose intensity and the number and timing of prescribed dose reductions and interruptions.

The study endpoints are described in [Section 4](#). The planned analyses are described in detail in Sections 10.4 to [10.6](#).

10.4 Safety Analysis

Safety will be assessed through summaries of AEs, changes in laboratory test results, changes in ECG/echocardiograms results and changes in vital signs. All patients who receive at least one dose of surufatinib will be included in the safety analysis (ie, the Safety Analysis Set - All Treated Population).

All AE data will be listed by individual patient and cohort. All AEs will be graded using the NCI CTCAE (v.4.03) severity grading system. All adverse events will be coded with

MedDRA. The frequency of AEs will be summarized by MedDRA System Organ Class (SOC), Preferred Term (PT), and NCI CTCAE grade.

Incidence rates of DLTs by SOC and PT will be summarized for DLT set defined as all treated patients who are evaluable for DLT assessment (see [Section 5.1.1.2](#)).

Changes in laboratory data will be summarized by grade using the NCI CTCAE, v.4.03. Selected vital signs and selected laboratory data may be plotted over time for each patient.

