7.1.8 Important Potential Risks

The important potential risks of surufatinib include the following: infection, intestinal obstruction, gastrointestinal perforation, myocardial ischaemia, cardiac failure, venous thromboembolism, arterial thromboembolism, and pancreatitis. One patient in the 2015-012-00US1 trial experienced grade 3 PRES, which was deemed related to study drug and was considered resolved. For more information, please see surufatinib IB.

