8.1.4 Cardiac Monitoring

Left ventricular ejection fraction (LVEF) assessed via echocardiogram or MUGA at Screening-Baseline and every 12 (± 1) weeks thereafter and at the end of study treatment. The modality of the cardiac function assessments must be consistent within a patient i.e. if echocardiogram is used for the screening assessment then echocardiogram should also be used for subsequent scans if required. The patients should also be examined using the same machine and operator whenever possible.

The 12-lead ECGs should be performed at screening, pre-dose and at 2 hours \pm 15minutes post surufatinib dose on Days 1 and 15 in Cycle 1, on Day 1 of each cycle from Cycle 2 and onward and at the end of study treatment. The QTcF interval will be closely monitored (See [Appendix 1](#)).

Test results will be reviewed by the investigator to determine patient eligibility at screening. Additional test and other cardiac monitoring will be provided as clinically indicated during the study.

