3.2.2. Secondary Objectives

The secondary objectives are:

- To evaluate the PK profile of multiple dose surufatinib in patients with advanced BTC, patients with advanced pNET, patients with advanced epNET, and patients with advanced STS.
- To evaluate the safety of surufatinib in patients with advanced BTC, patients with advanced pNET, patients with advanced epNET, and patients with advanced STS.
- To evaluate the anticancer activity of surufatinib in patients with advanced BTC, patients with advanced pNET, patients with advanced epNET, and patients with advanced STS.

Secondary Endpoints:

- Pharmacokinetic parameters, which include but are not limited to, C_{max} , T_{max} , first-order rate constant K_{el} , AUC, $t_{1/2}$, CL/F, V_z/F , accumulation ratio, and dose proportionality between AUC and dose and C_{max} and dose.
- Safety, as assessed by:
 - The frequency and severity of adverse events
 - Physical examination findings
 - Vital signs

- Laboratory test results (ie, hematology, chemistry panel, and urinalysis)
- 12-lead electrocardiogram
- Echocardiogram
- ORR, DCR, time to response (TTR), DoR, and percentage change in tumor size from baseline defined according to RECIST V 1.1.

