7.4. RETESTS, UNSCHEDULED VISITS AND EARLY TERMINATION DATA

In general, for by-visit summaries, data recorded at the nominal visit will be presented. Unscheduled measurements will not be included in by-visit summaries. Unscheduled measurements will contribute to worst-case summaries. In the case of a retest (visit-specific unscheduled visit number assigned), the latest non-missing measurement among all scheduled and unscheduled measurements for that visit will be used for by-visit summaries.

Early termination data of patients prematurely discontinued from study medication will be presented together with the end of treatment assessment for study medication completers.

By-patient listings will include scheduled, unscheduled, retest, and early discontinuation data.

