17.6.2. Echocardiogram

Echocardiography, including left ventricular ejection fraction (LVEF) assessment contains both quantitative results (%) and overall evaluation [Normal; Abnormal, Not Clinically Significant (ANCS); Abnormal, Clinically Significant (ACS)].

Actual value of echocardiography measured at each scheduled visit, change from baseline to each post-baseline

CCI

scheduled measurement will be presented by visit. Overall evaluation will be summarized separately.

All echocardiography results including change from baseline for LVEF and relevant information will be listed.

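### The SAP defines no worst post-baseline LVEF summary, so an LVEF fall found at an unscheduled test not tied to a visit enters no numeric LVEF table

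*Protocol*

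**What the plan says.** **Measurement.** Protocol 8.1.4 requires "Left ventricular ejection fraction (LVEF) assessed via echocardiogram or MUGA at Screening-Baseline and every 12" weeks (window 1 week), and again at the end of treatment. One modality is kept within a patient. The same section adds: "Additional test and other cardiac monitoring will be provided as clinically indicated during the study".

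**Endpoint.** The expansion-phase safety endpoints list "Echocardiogram" as a separate item (SAP 3.2.2, matching Protocol 4.2.4). Protocol 10.4 refers to "changes in ECG/echocardiograms results and changes in vital signs".

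**Analysis.** SAP 17.6.2 presents "Actual value of echocardiography measured at each scheduled visit", with change from baseline at each scheduled post-baseline measurement. The overall evaluation (normal, or abnormal with or without clinical significance) gets its own summary, and all echocardiography results are listed.

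**Rule for unscheduled data.** SAP 7.4: "Unscheduled measurements will not be included in by-visit summaries". The next sentence of that section admits them to worst-case summaries. A retest that carries a visit-specific number is an exception: the latest non-missing value for that visit is used.

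**Risk.** Protocol 7.1.8 includes among the important potential risks "myocardial ischaemia, cardiac failure, venous thromboembolism, arterial thromboembolism, and pancreatitis".

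**The concern.** A by-visit table of means and changes describes the typical patient at fixed times. It is a poor instrument for a safety signal that shows up in a few patients at unpredictable times, which is why the SAP pairs by-visit tables with worst-value summaries for other safety measures. For LVEF the second half of the pair is missing. SAP 7.4 sends unscheduled values to a kind of summary that SAP 17.6.2 never creates.

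Tests done because a patient has symptoms are the ones most likely to show a real fall. If they are left out of the numeric tables, a reader of the report cannot find the proportion of patients whose LVEF fell below a stated level, or by how much, without working through the listing patient by patient.

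**Working it through.** No figure in the plan needs reproducing. The check sets the rules side by side and follows one value through them.

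**1. Which safety measures have a worst-value summary?**

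| Measure | By-visit summary | Worst post-baseline summary | SAP section |
|---|---|---|---|
| ECG intervals, heart rate | Yes | Yes, against stated thresholds | 17.3, 17.3.2 |
| Laboratory values | Yes | Yes, shift to worst CTCAE grade | 17.2, 17.2.3 |
| ECOG | Yes | Yes, shift from baseline to worst | 17.6.1 |
| LVEF | Yes, scheduled visits | None defined | 17.6.2 |

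**2. Follow one LVEF result from a symptom-prompted test between visits.**

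- By-visit value and change: excluded (SAP 7.4 and 17.6.2).
- Visit retest exception: does not apply unless the test is assigned to a visit.
- Worst-case summary: SAP 7.4 would admit it, but none exists for LVEF.
- Overall-evaluation summary: the SAP does not say whether unscheduled results count. In any case this summary carries no LVEF value.
- Listing: included, if done by echocardiogram. MUGA is not mentioned.
- AE tables: included if the investigator reports an event (Protocol 10.4, SAP 17.1.1), by term, severity and relationship.

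So the result reaches no numeric LVEF table. The treatment of unscheduled values is also uneven. Before the first dose an unscheduled LVEF can serve as baseline (SAP 7.2), while after the first dose it is dropped from the by-visit table.

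**3. The retest rule.** Because the latest value for a visit is used, a low first reading followed by a higher visit-linked retest appears in the by-visit table only as the higher value. A worst-value table would show the low one.

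**4. How many scheduled values are there?** The 12-week interval is set against the approximate treatment durations in the protocol synopsis, with the SAP's 30.4375 days per month:

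- Arm A: 16 / 12 = 1.33, so 1 scheduled on-treatment value.
- Arm D: 4 × 30.4375 / 7 = 17.4 weeks; 17.4 / 12 = 1.45, so 1.
- Arms B and C: 11 × 30.4375 / 7 = 47.8 weeks; 47.8 / 12 = 3.99, so 3, or 4 using the 1-week window.

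Each count is in addition to the end-of-treatment value. Patients may stay on treatment longer, so these counts apply to the synopsis durations and are not ceilings. Over those durations, Arms A and D have one on-treatment value per patient in the by-visit table.

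**5. Is there a targeted AE table instead?** SAP Appendix 2 has special-interest groups for renal, haemorrhagic, hepatic, hypertensive, proteinuria and thyroid events. A few cardiac terms sit inside the hypertension and thyroid groups, but there is no cardiac failure group.

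**The case against.** The strongest reply is that little is really lost, and several parts of it stand.

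- **AE tables.** A symptomatic fall or cardiac failure reported as an event is tabulated for all treated patients, whatever the visit timing or imaging method, with further tables for serious events and those leading to dose change or withdrawal. A reader might infer that such falls enter no summary at all; the documents do not support that. What remains is that AE tables depend on reporting and give neither the LVEF change nor the proportion below 50%.
- **The patient stays in.** A reader might infer that patients with a prompted test are removed from the LVEF summary. They are not: SAP 7.4 leaves out the measurement only. Baseline, 12-weekly and end-of-treatment values remain, and early-termination data are shown with end of treatment. That last value is not a full substitute, since SAP 7.3 places the visit 30 ± 7 days after the last dose.
- **MUGA.** Protocol 8.1.4 has "LVEF) assessed via echocardiogram or MUGA at Screening-Baseline", while the SAP never mentions MUGA. It is tempting to conclude that MUGA patients reach no LVEF table. That is inference from silence: no text drops their values, SAP 17.6.2 refers to LVEF assessment, and the case report forms and output templates that would settle the matter are not in the reviewed text. Nor do the documents link choice of modality to outcome, so no bias follows.
- **Importance.** LVEF is one descriptive item within a secondary safety endpoint, the study has no formal hypothesis tests, and cardiac failure is a potential rather than an identified risk. This limits the weight of the point without removing it.

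**Conclusion.** The point holds in a narrow form that rests on explicit text in SAP 17.6.2 and 7.4. A post-baseline LVEF value from an unscheduled test not tied to a visit enters no numeric LVEF table, because the only summary that could take it is not planned. ECG, laboratory grades and ECOG are handled differently in the same SAP.

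The size cannot be stated. The documents give neither the number of unscheduled LVEF tests nor the number of patients followed by MUGA, so any percentage of missed falls would be invented. The by-visit summary is also not wrong for what it describes; it simply does not answer the question of how low LVEF went and in how many patients.

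The conclusion assumes that some clinically prompted tests take place, as the protocol allows, and that the unseen output templates do not already contain a worst-value LVEF table. Efficacy results are unaffected. The missing MUGA wording would not justify a change by itself and is worth fixing only alongside the table.

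**What to change.** Add one table to SAP 17.6.2: worst (lowest) post-baseline LVEF by dose level and disease cohort, using scheduled, unscheduled and end-of-treatment values. Show:

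- n (%) with LVEF below 50%. This is the limit in exclusion criterion 14, so eligible patients start at or above it and a value below it is a change.
- n (%) by size of fall from baseline, in categories that the sponsor fixes before database lock. The documents supply no cut-points.

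The denominator is patients with a baseline and at least one post-baseline LVEF.

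In the same section, state that LVEF by echocardiogram or MUGA is included, with modality shown. Because modality is fixed within a patient, change from baseline remains interpretable.

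Protocol 10.4 does not restrict the summary to scheduled visits, so the addition fits it. It can be recorded in SAP 4.4, as the extra ECG analyses were. The cost is one table and a sentence, with no new data collection.

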10.5 Pharmacokinetic Analysis

All patients whose plasma samples are collected for analysis of the plasma surufatinib concentration and derivation of PK parameters will be included in the Pharmacokinetic Analysis Set (PKAS).

A non-compartmental model analysis will be performed for plasma concentration data by central lab using WinNonlin (enterprise version). The following statistic data will also be reported: mean value, standard deviation, median value, minimum value, maximum value, geometric mean value, and geometric mean coefficient of variation.

The individual and mean pharmacokinetic parameters determined following analysis of the surufatinib concentration versus time data, will include, but not be limited to total plasma exposure (AUC_{0-∞}), C_{max}, CL/F, and V_z/F. The t_{1/2} will also be estimated. Mean, standard deviation (SD) and coefficient of variation (CV) will be presented. The actual times of plasma sample collection will be used in the determination of the pharmacokinetic parameters.

The methods for calculating pharmacokinetic parameters of surufatinib:

- C_{max}: the maximum observed plasma concentration over the sampling period, taken directly from the data.
- T_{max}: time at which C_{max} occurred, taken directly from the data.
- K_{el}: the first-order rate constant associated with the negative slope of the terminal portion of the log-linear concentration-time curve. A minimum of three points will be used.
- Area under the plasma concentration versus time curve (AUC) to be determined by the linear trapezoidal rule, where AUC_{last} is the AUC from time zero until the last concentration point and AUC_{0-∞} is the AUC_{last} + last concentration point divided by K_{el}.
- Half-life (t_{1/2}) to be determined according to t_{1/2} = 0.693/K_{el} where possible.
- CL/F: systemic clearance to be determined according to Dose/AUC_∞
- V_z/F: apparent volume of distribution, determined according to CL/F/K_{el}
- Dose Proportionality: to be evaluated by investigating the linearity of the relationship between AUC and dose, and C_{max} and dose.
- Accumulation ratio: AUC_{Day15}/AUC_{Day1} or AUC_{Day29}/AUC_{Day1}

Where the concentration data are missing, or listed as less than Lower Limit of Quantification, they will be regarded as zero (0) if occurring before C_{max}. After C_{max}, zero points will not be included in calculations.

Individual and mean surufatinib concentrations will be plotted by dose level.

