1 SYNOPSIS

Title	A Multi-Center, Open-Label, Clinical Trial to Evaluate the Safety, Tolerability, and Pharmacokinetics of Surufatinib (HMPL-012), Previously Named Sulfatinib in Advanced Solid Tumors
Short Title	Not Applicable
Acronym	Not Applicable
Phase	1/1b
Rationale	
There is an unmet medical need for new, safe and effective therapy for patients with advanced biliary tract cancer (BTC), advanced pancreatic neuroendocrine tumor (pNET), advanced extrapancreatic neuroendocrine tumor (epNET), and advanced soft tissue sarcoma (STS).
 
Surufatinib, discovered by Hutchison MediPharma International, primarily inhibits vascular endothelial growth factor receptor, fibroblast growth factor receptor, and colony stimulating factor 1 receptor, sparing many other kinases. Preclinical safety evaluation results supported a good safety profile for surufatinib.
 
Surufatinib has demonstrated statistically significant and clinically meaningful efficacy in clinical studies on patients with advanced cancer in China. This is a dose escalation and dose expansion study, to be conducted in a United States patient population to confirm the safety and efficacy results of clinical studies performed in China.

Target Population	Patients at least 18 years old with locally advanced or metastatic solid tumors for whom approved therapy either does not exist or has proven to be ineffective or intolerable. In the dose expansion phase, patients with histologically or cytologically documented, locally advanced or metastatic BTC that has progressed on standard first line chemotherapy (Arm A), low-to-intermediate grade (G1 or G2), well-differentiated, unresectable or metastatic pNET that has progressed on everolimus, sunitinib, or both (Arm B), low-to-intermediate grade (G1 or G2), well-differentiated, unresectable or metastatic epNET that has progressed on everolimus (Arm C), and advanced STS (Arm D) that has progressed on at least one line of standard therapy (if available), or refused standard frontline cytotoxic chemotherapy will be evaluated for enrollment.
Intervention	Surufatinib (HMPL-012), oral once daily (QD) to be taken with 200 mL water within 1 hour after breakfast.
Description of Sites	Approximately 8 to 15 sites in the United States and Europe.
Objectives and Endpoints	
Dose Escalation	

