2.2.2 Nonclinical Pharmacokinetics

After a single intravenous dose of 10mg/kg surufatinib in rats, the plasma elimination half-life of surufatinib was measured as 2.8 hours, and plasma clearance and apparent volume of distribution were 3.53 L/h/kg and 13.1 L/kg, respectively. Following dosing via oral gavage at low, medium and high dose levels, the mean value of time to reach maximum concentration was 3.0~4.2 hours. The oral bioavailability was observed to be dose dependent. At the dose level of 10 mg/kg, the bioavailability was just 9.9%. When the dose was increased to 40 mg/ml or above, the bioavailability exceeded 50%. The low bioavailability observed at the low dose level might be associated with the efflux by P-glycoprotein in intestinal epithelial cells.

After a single intravenous dose of 5 mg/kg in dogs, the plasma elimination half-life was 3.3 hours, and plasma clearance and apparent volume of distribution were 3.94 L/h/kg and 18.5 L/kg, respectively. Following a single oral dose of 5, 10 and 20 mg/kg, the mean value of time to reach maximum concentration was 3.5~4.5 hours. In the dose range of 5~20 mg/kg, surufatinib exposure (C_{max} and AUC_{0-t}) increased dose-proportionally. Feeding had no obvious effect on the extent and speed of surufatinib absorption. At the oral dose level of 10 mg/kg, the absolute bioavailability was 30.5%.

After administration via oral gavage in rats, surufatinib was distributed widely in various tissues mainly including lung, liver, spleen, adrenal gland, kidney, pancreas and stomach wall. The lowest drug concentration was observed in brain, indicating poor brain blood penetration. At 24 hours post-dose, concentrations in most tissues reduced to 10% or lower than the peak concentrations.

The results of [14C]-surufatinib excretion study revealed that surufatinib was mostly excreted via faeces (approximately 80% of the dose, including 40% for bile excretion), and a small amount was excreted via urine (approximately 10% of the dose).

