Prior to shipment, a PK sample requisition form (containing the details of each sample / label identification included in the shipment) will be prepared. All sample correspondence must contain the Study Number, Study Drug, and Site references (including emergency contact details and responsible shipment coordinator). All of the sample details on this log must correspond with the details included on the individual sample labels, as each sample label will be checked against the list by Centre Laboratories' sample coordination personnel. The log should be reviewed by the preparer and a second individual for accuracy and signed/dated by both individuals. (An example sample transfer sheet is used to document the general information regarding the shipment). To avoid sample mix-ups

or misidentification, the samples in the shipment will be sorted by patient number and sample time using segmented cartons.

Table 11 Pharmacokinetic Sampling Time Points

Visit Cycle and Day	Time Point
Cycle 1, Day 1	Pre-dose \leq 10 minutes
	Post-dose 1 hour (\pm 15 minutes)
	Post-dose 2 hours (\pm 15 minutes)
	Post-dose 4 hours (\pm 30 minutes)
	Post-dose 6 hours (\pm 60 minutes)
	Post-dose 8 hours (\pm 60 minutes)
Cycle 1, Day 2	Pre-dose \leq 10 minutes
Cycle 1, Day 15	Pre-dose \leq 10 minutes
	Post-dose 1 hour (\pm 15 minutes)
	Post-dose 2 hours (\pm 15 minutes)
	Post-dose 4 hours (\pm 30 minutes)
	Post-dose 6 hours (\pm 60 minutes)
	Post-dose 8 hours (\pm 60 minutes)
Cycle1, Day 16	Pre-dose \leq 10 minutes

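### Linear trapezoidal AUC across an unsampled 8–24 h window overstates AUC and understates CL/F if the human half-life is short; linear-up/log-down, reported beside the linear rule, is a cheap improvement

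*Protocol*

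**What the plan says.** Protocol 10.5 sets the integration rule: "Area under the plasma concentration versus time curve (AUC) to be determined by the linear trapezoidal rule". AUClast "is the AUC from time zero until the last concentration point", and AUC0-∞ adds the last concentration divided by Kel. CL/F is "systemic clearance to be determined according to Dose/AUC" to infinity, and Vz/F is CL/F divided by Kel. Kel is the terminal slope on the log scale: "A minimum of three points will be used". After Cmax, missing or below-quantification values are treated as zero and "zero points will not be included in calculations".

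In Table 11 (Protocol 8.4.2), the last sample on Cycle 1 Days 1 and 15 is "Post-dose 8 hours". The next is the pre-dose sample on Day 2 or Day 16. Dosing is "oral once daily (QD) to be taken with 200 mL water within 1 hour after breakfast", so that sample falls at about 24 h.

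AUC is a secondary endpoint in both phases (Protocol 4.1.4 and 4.2.4). SAP Sections 2 and 3.1.2 leave PK to a separate pharmacokinetics analysis plan, which was not among the documents reviewed.

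**The concern.** A straight line between two points on an exponentially falling curve lies above the curve. Over a 1–2 h gap the excess is small; over 16 h it may not be. The error passes into AUClast and AUC0-∞ and, inverted, into CL/F and hence Vz/F.

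Section 10.5 already treats the late decline as exponential, both in estimating Kel and in extrapolating beyond the last sample. Joining 8 h to 24 h with a straight line does not fit that assumption. Log interpolation on the falling part applies the same assumption inside the dosing interval, using the same samples.

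What is at stake is the absolute level of reported exposure and clearance, for example when set beside the exposures from trials in China that Protocol 5.1.1 and 5.4 mention.

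**Working it through.** The documents state no AUC, CL/F or human half-life, so there is no figure of the plan's own to reproduce.

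**Inputs from the documents.** Sampling times 0, 1, 2, 4, 6, 8 and about 24 h (Table 11); the AUC, Kel and CL/F definitions (Protocol 10.5); once-daily dosing.

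**Assumptions.** Human half-life varied from about 3 to 24 h; Tmax 2–4 h (1–4 h where stated); one-compartment oral model; quantifiable 24 h value. The only half-lives in the documents are animal values after a single intravenous dose: in rats "the plasma elimination half-life of surufatinib was measured as 2.8 hours", in dogs 3.3 h (Protocol 2.2.2).

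**Step 1: the 8–24 h segment alone, pure exponential decline.** With k = ln 2 / t½ and r = C24/C8 = 2^(−16/t½):

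- linear area = 16 × (C8 + C24)/2 = 8 × C8 × (1 + r)
- exact area = (C8 − C24)/k = C8 × (1 − r)/k
- ratio = 8k(1 + r)/(1 − r)

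| t½ | r | k (per h) | ratio | excess |
|---|---|---|---|---|
| 3 h | 0.025 | 0.231 | 8 × 0.231 × 1.025 / 0.975 = 1.94 | +94% |
| 6 h | 0.157 | 0.1155 | 8 × 0.1155 × 1.157 / 0.843 = 1.27 | +27% |
| 12 h | 0.397 | 0.0578 | 8 × 0.0578 × 1.397 / 0.603 = 1.07 | +7% |
| 24 h | 0.630 | 0.0289 | 8 × 0.0289 × 1.630 / 0.370 = 1.02 | +2% |

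**Step 2: whole-interval AUC0-24**, Tmax 2–4 h, each rule on the Table 11 times against a fine-grid AUC:

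| t½ | linear rule | linear-up/log-down |
|---|---|---|
| 3 h | +17 to +21% | −3 to −5% |
| 6 h | +9 to +10% | about −2% |
| 8 h | about +6% | about −1% |
| 12 h | about +3% | about −1% |
| 18 h | about +1% | about −1% |
| 24 h | under +0.5% | about −1% |

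**Step 3: AUC0-∞ and CL/F**, Tmax 1–4 h, AUC0-∞ = AUClast + Clast/Kel. The linear error is +12 to +21% at t½ 2.8 h, +7 to +9% at 6 h and at most +3% at 12 h. It reaches 10% only below a half-life of about 4.3–5.7 h, and 5% only below about 7–8.7 h. Because CL/F = Dose/AUC0-∞, an error of +12% gives 1/1.12 − 1 = −11%, and +21% gives 1/1.21 − 1 = −17%. Log-down removes 55–87% of the absolute AUC0-∞ error at half-lives of 2.8–6 h.

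**Step 4: robustness.**

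- With 15% log-normal noise, the root-mean-square error of AUC0-24 falls from 17.9% to 6.5% at t½ 4 h and from 10.7% to 6.9% at 8 h; at 24 h it is about equal (8.0% against 7.6%).
- With biexponential decline, a linear error of +4 to +8% becomes +1 to +3%.
- With a second peak after 10 h, the linear error is −4 to +6% and the log-down error −5 to −11%, so log-down is worse in most of these cases.
- The accumulation ratio is within about 0.5% of the true value under either rule.

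**The case against.** The strongest reply is that materiality hangs on a number nobody has shown. With no human half-life in the documents, the linear error could be anything from about 20% to nothing. A reader might take the animal half-lives and infer that this trial's AUCs are overstated by about a fifth. The documents do not support that: those are intravenous rat and dog values, with nothing to carry them over to oral dosing in patients. This stands, and the point is therefore conditional.

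Second, the error may remove itself where it looks largest. At t½ 3 h the 24 h level is 2^(−16/3) = 2.5% of the 8 h level. If that is below quantification it is dropped, AUClast ends at 8 h, and there is no 8–24 h line. The assay limit is not given. This stands too: the figures apply only to patients with a quantifiable 24 h value.

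Third, log-down is not free of error. It leaves about −1 to −5% at short half-lives and gives no material gain at 12 h or more. With Tmax 1 h and t½ 12 h it is slightly worse for AUC0-∞ (−1.7% against +1.1%). A second peak in the gap could make it worse still. Protocol 2.2.2 reports about 40% biliary excretion, which makes a second peak possible, though no document shows one in patients. This is the reason to report both rules.

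Fourth, the PK analysis plan may already settle the matter. If it names log-down, it and Protocol 10.5 need reconciling; if it is silent, the protocol wording governs.

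Finally, PK is a descriptive secondary endpoint with no hypothesis test. A reader might infer that between-patient variability is distorted or the RP2D undermined. The first was not calculated. For the second, Protocol 5.1.1 and 5.1.2 tie the declaration of the MTD and RP2D to dose-limiting toxicities in 2 of 6 evaluable patients at 400 mg, not to an AUC value.

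**Conclusion.** The point holds in a limited, conditional form. The linear rule and the 16 h gap are both in the protocol, and the direction is certain for a log-linear decline with a quantifiable 24 h value: AUC too high, CL/F too low. The size runs from about 17–21% of AUC0-24 at a half-life of 3 h, through 9–10% at 6 h and 6% at 8 h, to 3% at 12 h and negligible at 18–24 h or more. These figures rest on a one-compartment model with Tmax 2–4 h. The documents do not show where in this range patients fall. Absolute AUC and CL/F are affected; the accumulation ratio hardly is. This is a worthwhile low-priority improvement.

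**What to change.** In Protocol 10.5 and the PK analysis plan:

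- Use the linear-up/log-down trapezoidal rule for AUClast/AUC0-24 on Days 1 and 15.
- Use it for AUC0-∞ on Day 1 only. On Day 15, AUC0-∞ includes carry-over from earlier doses. In a one-compartment model with rapid input it exceeds the dosing-interval AUC by a factor of 1/(1 − 2^(−24/t½)): +14% at t½ 8 h, +33% at 12 h, +100% at 24 h. From about 8 h upward that is larger than the linear-rule error being removed. Section 10.5 does not say on which day AUC0-∞ is taken, so the wording should.
- Report the linear-rule AUC and the share of AUC from 8–24 h beside the log-down result. This shows how much depends on the interpolation, covers a possible second peak, and keeps comparability with PK results the Safety Review Committee has already considered.

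**Cost.** A wording change, a setting in the non-compartmental software and one extra table. It can be run on existing concentrations with no new samples. Changing Protocol 10.5 is an amendment that needs ethics review (Protocol 11.2), so it is best bundled with another. Interpolation does not replace data: with Tmax 2 h and t½ 4 h, a 12 h sample would cut the linear error in AUC0-24 from +14% to +3%.
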